#### **5.7.2. Analyses of Secondary and Exploratory Efficacy Variables**

The change and percent change from baseline in continuous secondary and exploratory efficacy endpoints will be analyzed using the same approach as that used for the analysis of the primary endpoint, unless specified otherwise.

The biomarker related continuous endpoint will be analyzed using a rank based ANCOVA model with treatment and relevant baseline as covariates. Post-baseline LOCF method will be used to impute the missing data. The comparison will be performed between dupilumab +SCIT vs SCIT.

The proportion of subjects who achieve SCIT maintenance dose (4000 BAU) during 16 weeks of treatment will be compared by Chi-square test between dupilumab + SCIT and placebo for dupilumab +SCIT groups. The maximal tolerated SCIT dose during 16 weeks of treatment and the local skin wheal size at approximately 15 minutes after each SCIT injection during 16 weeks of treatment will be summarized descriptively. If the wheel size is too small to measure after the SCIT injection, the diameter is set to zero.

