Dupilumab is a human monoclonal IgG4 antibody that inhibits interleukin-4 (IL-4) and interleukin-13 (IL-13) signaling by specifically binding to the IL-4R $\alpha$  subunit shared by the IL-4 and IL-13 receptor complexes. Blocking IL-4R $\alpha$  with dupilumab inhibits IL-4 and IL-13 cytokine-induced responses, including the release of proinflammatory cytokines, chemokines and IgE. IL-4 and IL-13 play key roles in the pathophysiology of allergic diseases, as demonstrated by dupilumab's efficacy shown in clinical studies in atopic diseases such as atopic dermatitis (AD), asthma, nasal polyposis (NP) and eosinophilic esophagitis. This is the basis for the rationale to evaluate whether dupilumab may enhance allergy immunotherapy. Dupilumab has clinically demonstrated down-modulation of the Type 2 pathway and has the potential to complement the immunoregulatory mechanisms of allergen immunotherapy. IL-4 and IL-13 are important cytokines that trigger class switching in B-cells (Lundgren M, 1989) and dupilumab has been shown to suppress serum total and specific immunoglobulin E (sIgE) over time in all studies where measured; serum total IgE decreased by ~30% after 12 weeks of weekly 300 mg treatment in AD; for sIgE, studies in AD and asthma patients show a ~40% reduction at week 16 and ~50% reduction at week 24 (Regeneron unpublished data). In a post-hoc analysis of a dupilumab dose-ranging study in moderate-to-severe asthma patients with comorbid allergic rhinitis, patients had a significant reduction in reported rhinitis symptoms with dupilumab compared to placebo. Because of these data and the role of IL-4 and IL-13 in immunoglobulin class switching, we anticipate that dupilumab as an adjunct to SCIT, will enhance the change of allergen specific IgG4/IgE ratio in SCIT + dupilumab treated subjects as compared to subjects treated with SCIT alone. In patients with AD, dupilumab modulated several Type 2 chemokines, including CCL17 (thymus and activation-regulated chemokine [TARC]) in serum and skin tissue, therefore we anticipate that dupilumab will modulate Type 2 chemokines and cytokines in subjects with a history of allergic rhinitis, which may improve tolerability of SCIT up-dosing (Beck, 2014) (Hamilton, 2014). A reduction in the production of Type 2 cytokines and chemokines by dupilumab is also likely to potentiate the reduction of provoked allergic rhinitis symptoms by SCIT.

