### 3.2.8. Rationale for Other Endpoints

#### 3.2.8.1. Ratio of Allergen-Specific IgG4 to IgE in Serum

Immunotherapy induces both cellular and humoral regulatory immune mechanisms. Humoral mechanisms involve the induction of allergen specific antibodies, especially of the IgG4 isotype, which is thought to have a protective effect against IgE-mediated allergic symptoms. IgG4 competes with IgE, blocking IgE-mediated effector cell activation, suppresses histamine release and inhibits antigen-presentation of IgE-allergen complex by dendritic and B-cells (James, 2012). The gradual increase in serum allergen-specific IgG4, IgE-blocking factor and decrease in allergen-specific IgEs have been associated with clinical desensitization in SCIT for grass (Shamji, 2012) and was consistently observed across different studies. At the start of SCIT, serum sIgG4s are low/undetectable. In response to the initiation of SCIT, a 2-fold increase in sIgG4 and a transient increase in sIgE is observed (Scadding, 2017) (Creticos, 1992)

(Suarez-Fueyo, 2014). An approximately 8-fold increase in the ratio of sIgG4/sIgE was associated with a reduction in symptoms induced by nasal allergen provocation after 1-year of SCIT (Scadding, 2017). A higher ratio of sIgG4/sIgE in patients tolerant to some allergens (eg, birch, cat, peanut) compared to their symptomatic controls was observed (Geroldinger-Simic, 2011) (Du Toit, 2013) (Burnett, 2013). Compared to the individual levels of sIgG4 or sIgE, the ratio of sIgG4/IgE is thought to be more reflective of the competition for allergen binding between IgG4 and IgE and has so far shown better correlation with clinical improvement. Given that the induction of sIgG4 and the suppression of sIgE is the most well-known phenomenon associated with immunotherapy and dupilumab has been shown to suppress specific IgE in past studies, we aim to test if skewing of sIgG4/IgE ratio will be one of the immunological effects of dupilumab as an adjunct to SCIT treatment.

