### **3.2.8.8. Rationale for Study Duration**

The time course of SCIT efficacy is not well established with limited data published regarding short-term efficacy endpoints. Clinical guidelines and experience indicate that symptomatic improvement can be demonstrated shortly after the patient reaches a maintenance dose (Ewbank, 2003). It is thought the onset of action could coincide with induction of sIgG4, which plateaus after reaching maintenance dose. While conventional up-dosing schedules require 8-12 weeks, we propose an 8-week cluster up-titration regimen to accelerate time to maintenance dose and onset of action of SCIT. Dupilumab has resulted in rapid, potent suppression of type 2 biomarkers within 4-12 weeks of treatment in all indications tested to date. Thus, a 16 week treatment duration is expected to be sufficient to evaluate the effects of dupilumab with and without SCIT.

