#### 10.4.3.2. Secondary Efficacy Analysis

The continuous secondary efficacy endpoints will be analyzed using the same approach as that used for the analysis of the primary endpoint.

The biomarker related continuous endpoint will be analyzed using a rank based ANCOVA model with treatment and relevant baseline as covariates. LOCF method will be used to impute the missing data.

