### 4.5.2. Secondary Efficacy Variables

The secondary endpoints are:

- Change from baseline in TNSS AUC post NAC over the first hour after the challenge (0-1 hr post peak TNSS) at week 17 for dupilumab + SCIT as compared to SCIT
- Change and percent change from baseline in TNSS AUC post NAC over the first hour of the challenge (0-1 hr post peak TNSS) at week 17 for dupilumab as compared to placebo

- Change and percent change from baseline in the TNSS AUC post NAC over the first hour of the challenge (0-1 hr post peak TNSS) at week 17 for dupilumab + SCIT as compared to dupilumab
- Change and percent change from baseline (last pretreatment measurement) to week 17 in serum Timothy Grass sIgG4 for dupilumab + SCIT as compared to SCIT
- Change and percent change from baseline (last pretreatment measurement) to week 17 in serum Timothy Grass sIgE for dupilumab + SCIT as compared to SCIT
- Change from baseline (last pretreatment measurement) to week 17 in log-transformed value of serum Timothy Grass sIgG4 to Timothy Grass sIgE ratio for dupilumab + SCIT as compared to SCIT

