## **5.12. Analysis of Biomarker Data**

All biomarker analyses will be performed on the FAS using all observed data. Descriptive statistics for the observed values, change from baseline and percent change from baseline values by treatment and visit will be provided for the biomarker variables.

The Wilcoxon signed-rank test will be used to test if the change or percentage change from baseline value is significantly different from zero. P-value will be reported.

Exploratory analyses for the difference between dupilumab groups and placebo on the change from baseline and percent change from baseline values will be performed using a rank-based ANCOVA model with treatment group and the relevant baseline values as covariate. Missing value will be imputed by LOCF method for visits between post-baseline to week 17. After week 17, no imputation will be made. P-value for difference between dupilumab +SCIT and SCIT will be provided.

Correlation of baseline serum Timothy Grass sIgE, Timothy Grass specific IgG, sIgG4, TARC and total IgE, absolute change or percent change at weeks 4, 8, and 17 from baseline in these biomarkers; with the following clinical endpoints will be explored using the Spearman's rho test. Both Spearman correlation coefficients and p-value will be reported. Correlation of baseline serum Timothy Grass sIgE, Timothy Grass specific IgG, sIgG4, TARC and total IgE with the following clinical endpoints will also be analyzed by the ANCOVA model with the clinical endpoint as the dependent variable and the baseline biomarker as the covariate, treatment group, and treatment group by baseline biomarker interaction as the factors. The missing values will be imputed using post-baseline LOCF. Similar correlation analysis will be performed for the subclasses of Timothy Grass sIgG other than sIgG4 pending on available data.

- Change and percent change from baseline in TNSS AUC post NAC over the first hour after the challenge (0-1 hr post peak TNSS) at week 17
- Change and percent change from baseline in TOSS AUC post NAC over the first hour after the challenge (0-1 hr post peak TNSS) at week 17
- Change and percent change from baseline (last pretreatment measurement) to week 17 in Skin Prick Test with Serial Allergen Titration, as measured by AUC of the average wheal sizes (diameter) after the challenge (early phase reaction)

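### Week-17 sIgG4, sIgE and log-ratio contrasts rest on LOCF alone, with no sensitivity analysis, although the protocol describes markers that change during treatment

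*SAP*

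**What the plan says.** SAP 5.7.2 analyses the biomarker endpoints with a rank-based ANCOVA, comparing dupilumab + SCIT with SCIT, and states: "Post-baseline LOCF method will be used to impute the missing data". Protocol 10.4.3.2 has the same rule: "LOCF method will be used to impute the missing data". SAP 5.12 sets its span: "Missing value will be imputed by LOCF method for visits between post-baseline to week 17". The same section opens with "All biomarker analyses will be performed on the FAS using all observed data", which does not sit easily with filling in missing values.

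The rule governs three sets of secondary endpoints in SAP 4.5.2. One is "Change and percent change from baseline (last pretreatment measurement) to week 17 in serum Timothy Grass sIgG4 for dupilumab + SCIT as compared to SCIT"; sIgE is listed the same way, and the log-transformed sIgG4/sIgE ratio as change only.

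Other endpoints are treated differently. SAP 5.7.1 uses 40-fold multiple imputation (MI) for a missing TNSS AUC, with LOCF and observed-data ANCOVA as sensitivity analyses. Those sensitivity analyses cover the primary endpoint only, and the summary table in SAP 10.1 has no biomarker row.

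**The concern.** LOCF assumes that a marker stays where it was last measured. The protocol describes change:

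- **sIgE on dupilumab** (Section 1): "for sIgE, studies in AD and asthma patients show a ~40% reduction at week 16 and ~50% reduction at week 24".
- **Start of SCIT** (3.2.8.1): "a 2-fold increase in sIgG4 and a transient increase in sIgE is observed".
- **sIgG4:** Section 3.2.4 places the rise after maintenance is reached. Section 3.2.8.8 speaks of "induction of sIgG4, which plateaus after reaching maintenance dose". Table 1 schedules the first 4,000 BAU dose for week 8.

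A subject last sampled before week 8 is therefore entered at week 17 with an up-titration value. The early-termination sample does not remove the problem. It is taken within 2 weeks of stopping, if possible (Protocol 7.3.2), and is assigned by study day. Week 17 means days 117-130 (SAP 6.3), so an earlier value is carried forward.

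If more subjects drop out of one arm than the other, the carried values shift one arm more. The sIgG4/IgE ratio is the mechanism that the protocol sets out to test, so an artefact here could be read as mechanistic support.

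**Working it through.** **Plan's own figure.** No power or dropout figure is given for the biomarkers. The only stated figure is 80% power for the TNSS AUC contrast. A two-sample t-test with difference 29, SD 35, n = 25 per arm and two-sided 0.05 gives 81.9%, so it reproduces. It supplies only n and alpha here.

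**Inputs from the documents.** sIgE on dupilumab is about -40% at week 16 and -50% at week 24. On starting SCIT, sIgG4 doubles; the sIgG4/sIgE ratio rises about 8-fold after one year. Samples fall at weeks 2, 4, 6, 8, 13 and 17 (read from a broken table).

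**Assumptions.**
- Dropouts' last samples are spread evenly over weeks 2, 4, 6, 8 and 13.
- sIgG4 rises 2-fold or, as a generous upper value, 8-fold, equally in both arms.
- The transient sIgE rise occurs in the SCIT-alone arm only. It peaks at week 8 at ×1 (none), ×1.5 or ×2, and is log-linear back to baseline at week 17.
- Dropout rates are assumed throughout.
- The week-17 reference value is the one expected had treatment continued.

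**Step 1: sIgE on dupilumab.** With a log-linear course, the log value at week t ≤ 16 is ln(0.6) × t/16. At week 17 it is ln(0.6) + [ln(0.5) − ln(0.6)]/8 = −0.534, or −41%.

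| Last sample (week) | 2 | 4 | 6 | 8 | 13 |
|---|---|---|---|---|---|
| Value carried to week 17 | −6% | −12% | −17% | −23% | −34% |

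The average carried value is −18%, a gap of 22.9 points. On the log scale the gap is −0.211 − (−0.534) = 0.323.

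**Step 2: sIgG4.** The share of the week-17 log rise that LOCF captures at weeks 2/4/6/8/13 is:
- 25/50/75/100/100% if sIgG4 plateaus at week 8 (average shortfall 30%);
- 12/24/35/47/76% if it rises to week 17 (average shortfall 61%).

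**Step 3: SCIT sIgE rise.** The average excess carried in the SCIT-alone arm is 0, 27.7 or 52.9 points for peaks ×1, ×1.5 and ×2. In logs it is 0, 0.239 or 0.408.

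**Step 4: shift in the contrasts.** Let p be dropout on the combination and q dropout on SCIT alone.
- sIgE percent-change contrast (true −41 points): shift = 22.9p − excess × q.
- Log-ratio contrast (true 0.53): shift = ln(fold) × shortfall × (q − p) − (0.323p − log excess × q).

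At p = 5%, q = 20%, the largest log-ratio shift is ln(8) × 0.612 × 0.15 − (0.016 − 0.082) = 0.191 + 0.066 = 0.26. The smallest is ln(2) × 0.30 × 0.15 − 0.016 = 0.02.

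| Dropout, combination vs SCIT | sIgE shift in points (×1, ×1.5, ×2) | Log-ratio shift |
|---|---|---|
| 10% vs 10% | +2.3, −0.5, −3.0 | −0.03 to +0.01 |
| 5% vs 20% | +1.1, −4.4, −9.4 | +0.02 to +0.26 |
| 20% vs 5% | +4.6, +3.2, +1.9 | −0.26 to −0.08 |

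**Step 5: type I error.** The rank ANCOVA was simulated with no treatment effect, 25 per arm, 3,000 runs per scenario, SD of log change 0.4 or 0.7, and dropout unrelated to outcome.

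| Dropout, combination vs SCIT | LOCF rejection rate |
|---|---|
| 10% vs 10% | 4.6-6.0% |
| 5% vs 20% | 5.4-13.5% |
| 5% vs 30% | 6.0-26.8% |

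Observed week-17 values alone rejected 4.6-5.5%. For 5% versus 20%, the low end is a 2-fold sIgG4 rise with a week-8 plateau and SD 0.7. The high end is an 8-fold rise to week 17 with SD 0.4. MI itself was not simulated.

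**The case against.** A reader might infer that LOCF flatters dupilumab. The documents do not support a direction. Carrying −18% instead of −41% understates the dupilumab effect on sIgE, and the sign of the ratio shift reverses with the arm that loses more subjects.

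A reader might also infer that every dropout carries a mid-titration value. That holds only for last samples before week 8. If sIgG4 plateaus as Protocol 3.2.8.8 says, the sIgG4 error from weeks 8 and 13 is about zero. For sIgE, week 13 gives −34% against −41%. Early-termination samples shorten the gap further.

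The −41% reference is not what a dropout would necessarily have shown. Stopping one study drug stops all (Protocol 7.3.2), so it is a had-treatment-continued value, and MI built on the on-treatment course targets the same quantity. This stands, and the estimand must be stated.

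Unequal dropout is inferred. Protocol Section 1 says only that dupilumab may improve tolerability. Sections 7.3.1 and 7.3.3.1 allow SCIT dose changes and temporary suspension, so intolerance need not become dropout.

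Finally, SAP 5.12 plans descriptive statistics on observed values by visit, so unimputed results will be visible. No observed-data test of the contrast is listed, however. These are secondary endpoints of a phase 2a trial without multiplicity control, and the primary endpoint already uses MI.

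**Conclusion.** The point holds as a risk, not as a demonstrated bias. LOCF is the only imputation for three sets of tested secondary contrasts, no sensitivity analysis is listed for them, and the constancy it assumes conflicts with the protocol. The conflict is clear for sIgE throughout treatment and for sIgG4 before week 8. For sIgG4 after week 8, Protocol 3.2.4 and 3.2.8.8 leave the course unclear.

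The sign and size of any bias are unknown. At equal 10% dropout the log-ratio shift is 0.03 or less and type I error stays near nominal. At 5% versus 20% the shift reaches 0.26 and type I error 13.5%, but only under the least favourable assumed course. All these figures rest on assumed dropout rates, marker courses and variances. The primary endpoint is unaffected. The change is worth making because it is cheap and the serial samples needed for it are already planned.

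**What to change.** In SAP 5.7.2 and 5.12:

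1. Multiply impute log-transformed sIgG4 and sIgE (40 imputations, as for TNSS AUC), using treatment, baseline and all scheduled post-baseline biomarker visits. Derive the ratio from the imputed values. Run the planned rank ANCOVA in each completed data set and pool.
2. Keep post-baseline LOCF and an observed-data rank ANCOVA as sensitivity analyses.
3. State that the imputation targets the week-17 value had treatment continued.
4. Reconcile the opening sentence of 5.12 on observed data with the imputation rule. State how randomised subjects with no post-baseline sample are handled, since post-baseline LOCF cannot fill them.

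The matching sentences in Protocol 10.4.3.2 and the synopsis should be aligned, or the change recorded in SAP 1.2.4. The cost is SAP text and modest programming. The one drawback is that pooling a rank-based test over imputations is less familiar than a single LOCF run. No extra data are needed, and Protocol Section 10 allows the SAP to be revised before database lock.

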### **5.7.3. Adjustment for Multiple Comparison**

There is no control for multiplicity.

## **5.8. Analysis of Safety Data**

The summary of safety and tolerability will be performed based on SAF and presented for each treatment group.

The safety analysis will be based on the reported AEs, clinical laboratory evaluations, physical examination, vital signs and 12-lead ECG.

Thresholds for treatment-emergent Potentially Clinically Significant Values (PCSVs) in laboratory variables and vital signs are defined in Section 10.3. Treatment-emergent PCSV is any PCSV developed or worsened in severity compared to the baseline during the treatment and follow-up period.

The time interval to detect any event or abnormality is between the first injection of study medication and EOS.

### **5.8.1. Adverse Events**

Listing of TEAEs, serious TEAEs, and TEAEs resulting in death and study drug discontinuation will be generated.

Number and proportions of patients reporting TEAEs will be summarized for overall during the study sorted by decreasing frequency of SOC and PT based on the overall incidence for the combined treatment groups.

Summaries of TEAEs will include:

- TEAEs
  - TEAEs by SOC/PT
  - TEAEs by SOC/HLT/PT
  - TEAEs by PT
  - Common TEAEs by SOC/PT (incidence with PT  $\geq 2\%$ )
  - TEAEs by severity by SOC/PT
  - Severe TEAEs by SOC/PT
  - Severe TEAEs related to dupilumab or placebo for dupilumab as assessed by the investigator by SOC/PT
  - Severe TEAEs related to SCIT or placebo for SCIT as assessed by the investigator by SOC/PT
  - Severe TEAEs related to study procedure as assessed by the investigator by SOC/PT
- Serious TEAEs by SOC/PT

- Serious TEAEs by SOC/PT
- Serious TEAEs by SOC/HLT/PT
- Serious TEAEs related to dupilumab or placebo for dupilumab as assessed by the investigator by SOC/PT
- Serious TEAEs related to SCIT or placebo for SCIT as assessed by the investigator by SOC/PT
- Serious TEAEs related to study procedure as assessed by the investigator by SOC/PT
- TEAEs leading to permanent discontinuation from study treatment by SOC/PT
- Death by SOC/PT

In addition, separate summary will be provided for the TEAE caused by SCIT or placebo SCIT injection.

Number of patients with dupilumab/placebo and SCIT/placebo reactions will be summarized as follows.

- Dupilumab/placebo for dupilumab injection reaction:
  - by preferred ISR term
  - by adverse event preferred term.
- SCIT/Placebo for SCIT injection reactions
  - by preferred ISR term for early local, late phase, and overall study
  - by adverse event preferred term for early local, late phase, and overall study
- SCIT/placebo for SCIT reactions
  - by reaction type and toxicity grade
  - by adverse event preferred term.

Number and proportion of patients reporting pre-treatment adverse events will be tabulated by SOC and PT.

### **Subgroup analysis**

Subgroup analysis will be performed for TEAE except injection reactions.

#### **5.8.2. Analysis of Adverse Events of Special Interest**

The adverse events of special interest (AESI) will be summarized by AESI category (see Section 10.4) and HLT/PT.

In addition, separate summary will be provided for the AESI caused by SCIT or placebo SCIT injection.

### **5.8.3. Clinical Laboratory Measurements**

Laboratory measurements include clinical chemistry, hematology and urinalysis results, and will be converted to standard international units. Summaries of laboratory variables will include:

- Descriptive statistics of laboratory result and change from baseline by visit
- The number (n) and percentage (%) of patients with abnormal lab value during study whose baseline values are normal (overall and per each lab parameter)
- The number (n) and percentage (%) of patients with treatment-emergent PCSVs
- Shift tables based on baseline normal/abnormal and other tabular and graphical methods may be used to present the results for parameters of interest

Listing of all laboratory parameters normal range, abnormal flag and treatment-emergent PCSV by patient and visit will be provided.

### **5.8.4. Analysis of Vital Signs**

Summaries of vital sign variables will include:

- Descriptive statistics of vital sign variables and change from baseline by visit
- The number (n) and percentage (%) of patients with treatment-emergent PCSV
- Shift tables based on baseline normal/abnormal and other tabular and graphical methods may be used to present the results for parameters of interest

Listings of vital sign will be provided with flags indicating the treatment-emergent PCSVs.

### **5.8.5. Physical Exams**

The number (n) and percentage (%) of patients with abnormal physical exams will be summarized at baseline, end of treatment period and end of study by treatment group. A summary of treatment-emergent abnormal findings will be provided.

